3.1.1 Risks associated with existing cough relief treatments

In 2007, the Nonprescription Drug Advisory Committee to the Food and Drug Administration (FDA) and Paediatric Committee voted for immediate action against the use of cough and cold medicines in children under the age of six because of their side-effects [1].

FDA does not recommend the use of these products in children below two years of age and withdrew some OTC cough products or restricted their use in children, especially those under the age of two years due to serious and life-threatening adverse effects [4, 11, 12]. Health Canada does not recommend their use in children below the age of six.

The risks and benefits of OTC cough remedies for children were reassessed by the Medicines and Healthcare products Regulatory Agency (MHRA) in 2009 [13], following which it was concluded that antitussives (dextromethorphan and pholcodine), expectorants (guaifenesin and ipecacuanha), nasal decongestants (ephedrine, oxymetazoline, phenylephrine, pseudoephedrine, and xylometazoline) and antihistamines (brompheniramine, chlorphenamine, diphenhydramine, doxylamine, promethazine, and triprolidine) should be prohibited in children under 6 years of age. These products may be administered in children between 6-12 years, subject to basic principles of best care and available in pharmacies where advice can be given.

3.1.2 *Glycerol as an effective and safe alternative for dry cough management*

The WHO [9] and MHRA [13] recommend the use of soothing products in children under the age of 6 years as an alternative to medicinal products with a negative benefit/risk ratio. Soothing syrups that contain demulcents like glycerol, have been reported to be frequently used and safe and it has been concluded that their use should be encouraged in children. The effect of the demulcents is attributed to the “coating” or lubrication of the posterior pharynx.

Glycerol does not have any known pharmacological actions, and its efficacy is related to its physical and chemical properties:

- Glycerol **coats** and **lubricates** the pharyngeal surface (demulcent and lubricant properties), thus helping in reducing the friction between moving surfaces while swallowing and speaking.
- Inflamed mucosal surfaces in the pharynx may also be soothed by the **moisturizing** properties of glycerol.
- Glycerol may also decrease the volume of proteins on the pharyngeal mucosa, which may contribute to the **lubricant** effect [4].
- The **sweet** taste in cough syrups has been suggested to influence the production of endogenous opioids and therefore modulate cough at the level of the nucleus tractus solitarius [4].

The safety profile of glycerol is well known and has been documented since the beginning of its use in therapy, as an excipient in medicinal products or as an ingredient in the agro-alimentary industry. No significant toxicity has been reported following prolonged use of glycerol in humans. Glycerol is rapidly incorporated in standard metabolic pathways where it is completely bio-transformed by the body to endogenous compounds.

3.1.3 *Rationale*

Petit Drill is a clear and colorless syrup, consisting of glycerol (0.75mL/5mL or 15% v/v) presented in an amber glass bottle of type III (Eur. Pharm.3.2.1.), intended to be filled with 125 mL solution, with polypropylene child resistant closure. A 5 mL measuring pipette is included with Petit Drill, for dosing the oral solution.

Petit Drill was initially CE marked in 2013 under the Medical Devices Directive 93/42/EEC as Class I medical device. Due to new classification rules under the Regulation (UE) 2017/745 (MDR), it has been upgraded to Class IIa.

The clinical evaluation of this device has been categorized as a “Well Established Technology” according to MDCG 2020-6 (April 2020). Nevertheless, Pierre Fabre Médicament wishes to generate its own clinical data of this product in a real-life context, in order to support the clinical evaluation.

3.2 **Evaluation of relevant pre-clinical assessment**

The toxicological profiles of all ingredients were evaluated on the basis of the quantitative formulation of Petit Drill cough syrup. All of the ingredients in the Petit Drill cough syrup are well characterized in analytical, microbiological and toxico-pharmacological contexts. A biological evaluation of Petit Drill cough syrup has been conducted in conformity among others to the requirements of EN ISO 10993-1, EN ISO 10993-5, EN ISO 10993-9 and EN ISO 10993-10.

Results from the literature review performed on each component to evaluate the different biological endpoints identified in the risk management process according to EN ISO 10993-1, indicate that Petit

Drill cough syrup is not expected to induce cytotoxicity, sensitization or irritation. The local tolerance of the medical device was confirmed in biocompatibility studies (Biological Evaluation Report DT-034-PFM-630).

3.3 Evaluation of relevant clinical data

3.3.1 *Description of the pathology*

Coughing is one the body's natural, necessary reflexes to clear the respiratory tract. There are different kinds of cough: chesty cough, called "productive", associated with expectorations (mucus secretions), or dry cough, called "non-productive", without expectoration. Dry cough is accompanied by a stinging sensation in the throat which generally intensifies at night, deteriorating the patient's quality of life.

3.3.2 *Data issued from clinical published studies on similar devices*

No clinical trials on demulcent glycerol-based syrups are available in the pediatric population affected by acute cough. A single sponsored limited randomized, placebo-controlled trial investigating glycerol in adult patients suffering from dry cough is cited in the systematic review conducted by the Italian Society of Pediatric Allergy and Immunology for Acute cough in children and adolescents published in 2021 [14]. This trial was sponsored by Naturveda Laboratory [4]. The experimental device is described as a hypertonic, highly osmotic, filmogen glycerol-based spray. The main inclusion criteria were: patients male and female in the 18-65 years age group presenting all clinical signs and symptoms of severe dry cough, sore throat with pain, and inflammation. The authors report that the group receiving the experimental filmogen glycerol-based spray showed a significant decrease in the mean scores of dry cough severity and frequency, throat pain, irritation, swelling, and redness when compared to saline placebo spray. No further details are given for the experimental formula. It is unknown if this experimental spray has obtained "market clearance".

Although, no clinical data are available in the pediatric population, cough syrups containing glycerol are promoted as the first-choice of cough treatment in infants and children up to 6 years old by health organizations (such as the WHO [9] and MHRA [13]) and professional guidelines.

Evidence-based reviews, systematic reviews and guidelines demonstrate the physiological effect of glycerol demulcent, thus establishing the ability of the demulcent to soothe the throat and to reduce symptoms of coughing.

3.3.3 *Data issued from clinical investigations on the device*

Pierre Fabre participated in the MAGICIA study [15] (MAnagement of couGh for Infants and Children during Infections of Airways). This study aimed at assessing the impact of acute cough on patients' and parents' sleep and children's activities in four European countries (Greece, Poland, Belgium and Portugal). MAGICIA study [15] was not designed explicitly for the evaluation of Petit Drill (known as Balsokids in Belgium). The benefits of Petit Drill could not be evaluated in the MAGICIA study because of the concomitant use of other medications in included patients.

The MAGICIA had a follow-up period of one week. The main objective of the study was to assess the impact of acute dry or mixed cough on the patient's and parents' sleep and activities. Secondary objectives included: evaluation the social impact of acute cough, description of symptoms associated with acute cough, of the therapeutic management of acute cough by pediatricians and general practitioners in each country, of cough evolution on one-week follow-up, of parents' observance and

satisfaction with treatment and therapeutic management, and of the profile of patients suffering from acute cough.

Children aged six months to six years visiting their general practitioner or pediatrician for common upper respiratory infections associated with acute dry or mixed cough, for up to three days before physician examination, were included. Exclusion criteria included receipt of antibiotics or corticosteroids during the past two weeks, diagnosis of chronic disease and need for hospitalization. These criteria aimed at including only patients with acute banal cough secondary to common viral infections without complications.

Ethical approval of this study was obtained from the relevant local ethics committees in Belgium, Portugal and Greece. Ethics approval was not required in Poland. Parental written informed consents were obtained, and all data were stored in an anonymous form.

The study included 1239 children (mean age: 3.1 ± 1.7 years) aged six months to six years. Medicinal products were often prescribed (83.6–99.6% of the patients), mainly demulcent syrup (except in Portugal) and antipyretics, while active antitussives with pharmacological agents were less often prescribed. In Portugal, a high proportion of patients (46.5%) received antibiotics compared to the three other countries. Petit Drill (or Balsokids) was reported as having been taken by patients in 218 children (49.6%) in Greece, 257 (55.3%) in Poland, 73 (47.7%) in Belgium and in none in Portugal; that is, a total of 548 patients of $3.1 (\pm 1.7)$ years, (44.2% of the cohort of 1239).

As most of the children (n=474) received other medications as well, it was not possible to evaluate the efficacy of glycerol syrup. However, 115 patients were prescribed only saline rinses and glycerol syrup as a treatment for cough, and 74 took only glycerol syrup between D0 and D7. The profile of the patients receiving glycerol syrup alone seems to be children with fewer symptoms such as fever, runny nose, nasal congestion, body aches, sore throat or ear pain, diarrhea, vomiting or reduced appetite. Compliance was high; 82.1% in Greece, 96.8% in Poland, 91.6% in Belgium and 89.3% in Portugal. When Petit Drill was prescribed, compliance was 83% in Belgium, 91% in Poland and 95% in Greece; this brand was not prescribed in Portugal.

Overall, at D0, cough frequency was reported as occasional in 26.9% of patients; frequent in 60.1%, and almost permanent in 12.9%. This decreased over time, being occasional at D7 in 89.8% of patients, frequent in 9.4% and almost permanent in 0.9%. At D0, cough intensity was mild in 23.7% of patients, moderate for 54.3% and severe for 22.0%, while these frequencies were 87.6%, 10.6% and 1.8%, respectively at D7.

Parents' satisfaction was assessed using the Client Satisfaction Questionnaire which includes eight questions (CSQ-8) related to initial information and advice, therapeutic management, with score ranging from 8 (very dissatisfied) to 32 (very satisfied) or on a visual analogue scale (0–10). At D7, the CSQ-8 scores evaluating parents' satisfaction ranged from 17 to 32 (maximum value of the score). The mean score in the three countries using the CSQ-8 was 27.8/32. Specifically, the mean CSQ-8 score was 29.5 in Greece, 28.3 in Poland and 21.7 in Belgium. In Portugal, satisfaction was assessed with a visual analogue scale and the mean score was 9.2 out of 10. The mean CSQ-8 score assessing parents' satisfaction for the population of children who received only glycerol syrup was 29.6 (out of 32), which was slightly higher than the country-wise mean satisfaction scores obtained in children who also received other treatments (21.7–29.5).

No complaints or vigilance cases related to the intake of glycerol syrup have been reported in any of the four countries. Additionally, this study confirms the absence of undesirable side effects due to possible interactions of demulcent syrups with drugs.

3.3.4 Safety data recorded from vigilance records

The tested product is already CE marked and has been on the market in several European countries since 2013. Up to 31-Aug-20232023, 47 cases were received for the tested product. Only 11 cases were associated with adverse reactions and all were assessed as non-serious.

The recorded safety data did not highlight any safety concern and showed good tolerability of the product.

3.4 Clinical development stage

This is a post-market clinical investigation, which aims to confirm clinical safety and performance data on the Petit Drill® Syrup.

4 RISKS AND BENEFITS OF THE INVESTIGATIONAL DEVICE AND CLINICAL INVESTIGATION

4.1 Anticipated clinical benefits

The anticipated clinical benefits are not different to those claimed in the IFU of the device. Petit Drill® Syrup soothes the irritation associated with dry cough by coating and moisturizing the throat. Due to its composition, Petit Drill® Syrup forms a protective film and moisturizes the throat, which makes it possible to calm the irritation and sore throat associated with dry cough.

4.2 Anticipated adverse device effects

Risks associated with the investigational device and its related clinical procedure shall be estimated in accordance with EN ISO 14971 prior to design and conduct of a clinical investigation (see Annex H of EN ISO 14155-2020). The risk assessment shall include or refer to an objective review of published and available unpublished medical and scientific data.

A summary of the benefit-risk analysis shall be disclosed in the relevant clinical investigation documents. The CIP shall include all anticipated adverse device effects and a rationale for the related benefit-risk ratio (see Annex A of EN ISO 14155-2020).

The risk assessment is provided in the Petit Drill Product Risk Management document DT-034-PFM-520-01, which is provided in ANNEX II: DT-034-PFM-520-01 Product risk management.

4.3 Risks associated with participation in the clinical investigation

The participants in this clinical investigation will not be exposed to any additional risks than those disclosed in the above sections, as this device is intended to be used as described in the IFU and in real-life practice.

4.4 Possible interactions with concomitant medical treatments

None known to date.

4.5 Actions to control or mitigate risks

These actions have been detailed in the Petit Drill Product Risk Management document DT-034-PFM-520-01, which is provided in ANNEX II: DT-034-PFM-520-01 Product risk management.

Most identified risks could be mitigated by following the instructions for usage and safe storage of the device, that have been elaborated in the IFU (ANNEX I: IFU).

4.6 Risk-to-benefit rationale

There will be no additional benefits or risks to the patient participating in the investigation, as it is a real-life observational study in which the device will be used per the IFU.

The results of this investigation would be essential for obtaining clinical data on device performance and safety, which will be utilized to support the clinical evaluation of the device as it is upgraded from a Class I to a Class IIa device, per the MDR, as explained in section 3.1.3.

No potential threats to this observational study have been identified, and no interactions with concomitant interventions are anticipated, other than those addressed in sections 4.2 and 4.3.

5 OBJECTIVES AND HYPOTHESES OF THE CLINICAL INVESTIGATION

The objective of this investigation is to obtain real-life clinical safety and performance data to support the current clinical evaluation of the Petit Drill device.

5.1 Objectives

5.1.1 *Primary objective*

To assess the performance of the Petit Drill medical device in the treatment of throat irritation (sore throat) associated with dry cough in infants starting at 6 months of age and in children up to 6 years of age.

5.1.2 *Secondary objectives*

- SO1. To describe the clinical and sociodemographic characteristics of children using Petit Drill.

The following secondary objectives will describe the performance and clinical benefit of Petit Drill in terms of:

- SO2. Changes in nightly cough frequency, severity, bothersome for the child, and ability to sleep for child and parent(s) throughout the 3 day-treatment;
- SO3. Changes in daily cough severity;
- SO4. Evolution of Quality of life.

The following secondary objectives will describe the use and safety of Petit Drill:

- SO5. Adherence to use of Petit Drill Syrup;
- SO6. Parents' satisfaction with Petit Drill use;
- SO7. Safety of the Petit Drill medical device in infants aged from 6 months to children up to 6 years of age.

5.1.3 *Exploratory objectives*

- SO8. To describe the dispensing modalities of Petit Drill by age group;
- SO9. To describe the study objectives (except SO8) according to child's range of age.

5.2 Hypotheses (if applicable)

Since this is an observational study, there are no formal hypotheses to test.

5.3 Risks and anticipated adverse device effects to be assessed

No additional risks or anticipated device effects were observed since the first CE mark application, apart from the ones already known or identified. Clinical safety data for Petit Drill will be obtained for the first time as part of a clinical investigation.

6 CLINICAL INVESTIGATION DESIGN

6.1 Type of clinical investigation

This will be an observational, prospective, single-arm descriptive clinical investigation, monocentric with national (French) patient pre-screening, which will not mandate or recommend any additional interventions or in-person visits. Since Petit Drill is an OTC treatment, patient contact, eligibility pre-screening will occur via pharmacies selling this device. Enrolment of the patients will be conducted remotely by the investigators (General Practitioners) of the Clinical Investigation Centre CEN Experimental located in DIJON (France).

All decisions regarding the treatment of included patients could be made by the investigators, dispensing pharmacist, and prescribing physician where applicable. All patients will be treated according to the local clinical practice and their parent/legal guardian will be instructed to fill questionnaires via a mobile application at specific timepoints.

The investigation and data collection are patient centered. The secure mobile application for PRO NursTrial® will be used to allow parents/ legal guardians to record the following data:

- Any AEs that may occur during the 3-day/3-night follow-up period;
- The number of times Petit Drill was administered to the patient on a daily basis;
- Patient-reported outcomes (PRO) – questionnaires to be filled by the patient to provide their assessment of the performance and useability of the device and their quality of life.

6.2 Bias minimization

- 1) **Site and patient selection bias:** Parent/legal representative of patients who refuse to participate may limit the representativeness of the study results. A screening log (see section 6.4) will be maintained, which will capture selected details from patients who were excluded or who parent/legal representative refused to participate, in order to counter this limitation. Another aspect is that this device can be purchased online, whereas recruitment will only be carried out via pharmacies. Therefore, patients who use Petit Drill syrup through online purchases will not be covered by this study.
- 2) **Attrition bias:** patients lost to follow-up are the main source of attrition bias in cohort studies. This can threaten sample representativeness if too many patients are lost to follow-up or if they differ from patients continuing follow-up (such as in their baseline characteristics or in their outcomes). To minimize any risks and potential impact, efforts will be undertaken to collect the data from the lost-to-follow up patient's most recent data recording, and investigators will be encouraged to contact the patient for a discontinuation assessment. Baseline characteristics of patients lost-to-follow up and those who completed the investigation may also be described to assess representativeness. Nevertheless, the follow-up period for this investigation is very short (3 days), the mobile application will send alerts resulting in parent/legal representative recall. Taken together, these measures are expected to minimize attrition bias.
- 3) **Recall bias:** is an inherent limitation of recollections from events or experiences from the past. This may apply to data collected for certain time periods in the past, such as the onset of improvement following treatment administration from the previous night. Since the periods of recall for this investigation will be very short, the impact of this bias will be minimized. Additionally, parents will be briefed on important timepoints from which data is to be retained so they are aware of the most

important information that needs to be retained for recording. As just mentioned above, missing data will result in alerts and recall of parent/legal representative.

4) Measurement error and missing data: This investigation relies on the patients' parents recording data for most study outcomes. Since they are not trained professionals and not used to responding to medical questionnaires, human error is to be anticipated in the estimation of numerical data, in the interpretation of questionnaires and in the recording of information. Measures will be put in place during eCRF and the mobile application NursTrial® to minimize these errors. The following quality checks are anticipated:

- Limiting the use of free fields for data entry – limiting responses to multiple choice questions, or list selection;
- Prompts and reminders in case of missing data.

In case of missing data or loss to follow-up, sensitivity analyses could be carried out to estimate the impact of missing data on the primary outcome.

6.3 Outcomes

6.3.1 Primary outcome

The primary outcome will be the percentage of children with a 3 point-decrease (minimal clinical significance) of the Pediatric Cough Questionnaire (PCQ) total score from baseline after up to 3 day-treatment with Petit Drill.

The PCQ refers to a past night recall of 5 questions, each scored from 0 "Not at all" to 5 "Extremely" using a 6-point Likert scale. PCQ Total score consists of the sum of each score and ranges from 0 to 25.

Baseline value will rate the night before the first day of treatment with Petit Drill, and will be recorded at inclusion (D1).

Final value will rate the night following 3 day-treatment or the night following the day of stopping the treatment, and will be collected on the next morning.

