	
 ○ Angina, otitis, or sinusitis; ○ Persistent cough lasting more than 3 weeks, whatever the etiology; ○ Gastrointestinal pathology, involving vomiting, nausea, or diarrhoea. 
 • EC2. With ongoing use of paracetamol and/or homeopathic products against cough; • EC3. Having had corticosteroid treatment, antibiotics, antihistaminic or any cough medication (such as, but not limited to, Phytoxil, Arkotoux) in the previous 15 days since inclusion; • EC4. With a brother/sister already included in the present clinical investigation*; • EC5. Enrolled in another clinical trial or being in a period of exclusion from a previous clinical trial. 
* If several children are eligible in the same household, only one will be enrolled at random.

Study endpoints/outcomes	
Primary outcome:
 
The primary outcome will be the percentage of children with a 3 point-decrease (minimal clinical significance) of the Pediatric Cough Questionnaire (PCQ) total score from baseline after up to 3 day-treatment with Petit Drill.
 
The PCQ refers to a past night recall of 5 questions, each scored from 0 “Not at all” to 5 “Extremely” using a 6-point Likert scale. PCQ Total score consists of the sum of each score and ranges from 0 to 25.
 
Baseline value will rate the night before the first day of treatment with Petit Drill, and will be recorded at inclusion (D1).
 
Final value will rate the night following 3 day-treatment or the night following the day of stopping the treatment, and will be collected on the next morning.
 
Secondary outcomes:
 
 • SO1. Baseline clinical and sociodemographic characteristics of children will be summarized using descriptive statistics. 
Secondary criteria related to the performance and the clinical benefit of Petit Drill will be described as follow:
 
 • SO2. Score global and score of the 5 items of PCQ (Q1: cough frequency, Q2: sleep disturbance of the child, Q3: sleep disturbance of the parent, Q4: cough severity, Q5: degree of bothersomeness to the child) will be described after 1, 2 and 3 day-treatment with Petit Drill. The percentage of children with a 3 point-decrease of PCQ total score from

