6.3.2 Secondary outcome(s)

- SO1. Baseline clinical and sociodemographic characteristics of children will be summarized using descriptive statistics;

Secondary criteria related to the performance and the clinical benefit of Petit Drill will be described as follow:

- SO2. Score global and score of the 5 items of PCQ (Q1: cough frequency, Q2: sleep disturbance of the child, Q3: sleep disturbance of the parent, Q4: cough severity, Q5: degree of bothersomeness to the child) will be described after 1, 2 and 3 day-treatment with Petit Drill. The percentage of children with a 3 point-decrease of PCQ total score from baseline at 1 and 2 day-treatment with Petit Drill will be described;
- SO3. Daily cough severity will be measured using visual analogue scale (VAS) ranging from 0 (no cough) to 100 (worst cough) in response to "Yesterday, how was the cough of

my child during the day?", measured VAS after 1, 2 and 3 day-treatment with Petit Drill. the evolution of scores from baseline will be described;

•SO4. Scores of the Parent-proxy Children's Acute Cough-Specific Questionnaire PAC-QoL (global and dimensions) will be collected at baseline (D1) and after 3 day-treatment with Petit Drill (morning D4), or on the next morning of the last day of treatment. The evolution of scores from baseline will be described.

Secondary criteria related to the assessment of use and the safety of Petit Drill will be described as follow:

- SO5. The mean (SD) number of times Petit Drill was administered in each 24-hour period from the first (D1) to the third (D3) day of treatment initiation will be described;
- SO6. Parent's satisfaction with Petit Drill use will be described using a questionnaire, and responses measured using Likert scales. Responses will be presented as percentages;
- SO7. Safety will be assessed by the analysis of:
 - Adverse events (frequency, severity, emergence, and causal relationship of adverse events) tabulated according to IMDRF terms (International Medical Device Regulators Forum, Annex E). Number and percentage of relevant AEs during treatment with Petit Drill, defined as all SAEs or AEs related to the device, and any AEs of special interest;
 - Number and percentage of device deficiencies.

6.3.3 *Exploratory outcomes*

- SO8. The percentage of children receiving Petit Drill with or without physician prescription will be described by two age groups: from 6 months to 12 months old and from 13 months old to 6 years of age;

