PAC-QoL (to be recorded by the parent/legal representative in the NursTrial® app with the help of the investigator)	
1-Were you worried/concerned about your child's cough becoming worse?	1- very, very worried and concerned
	2- very, worried and concerned
	3- fairly, worried and concerned
	4- somewhat worried and concerned
	5- a little worried and concerned
	6- hardly worried and concerned
	7- not worried and concerned
2-Did you feel tired or exhausted because of your child's cough?	1- all the time
	2- most of the time
	3- quite often
	4- some of the time
	5- once in a while
	6- hardly any of the time
	7- none of the time
3-Were you worried/concerned about the effects of your child's cough on him/her?	1- very, very worried and concerned
	2- very worried and concerned
	3- fairly, worried and concerned
	4- somewhat worried and concerned
	5- a little worried and concerned
	6- hardly worried and concerned
	7- not worried and concerned
4-Were you worried/concerned about the cause of your child's cough?	1- very, very worried and concerned
	2- very worried and concerned

Pierre Fabre

CLINICAL INVESTIGATION PLAN (CIP)

Table 3: Variables to be collected during patient follow-up by the parent/legal representative

Outcome	Suggested schedule	Variables
For primary outcome and secondary performance outcome 1: PCQ global and scores of the 5 items Q1, Q2, Q3, Q4 and Q5	D2 – first thing in the morning after 1 st night of treatment D3 – first thing in the morning after 2 nd night of treatment D4 – first thing in the morning after 3 rd night of treatment	0 – Not at all 1 – Occasionally 2 – A little 3 – Somewhat 4 – Very much 5 – Extremely
For secondary performance outcome 2: Daily cough severity	D2 – first thing in the morning after 1 st night of treatment D3 – first thing in the morning after 2 nd night of treatment D4 – first thing in the morning after 3 rd night of treatment	0-100 evAS value
For secondary clinical benefit outcome: PAC-QoL	D4 – first thing in the morning after 3 rd night of treatment	1- all the time or very, very worried and concerned 2- most of the time or very, worried and concerned 3- quite often or fairly, worried and concerned 4- some of the time or somewhat worried and concerned 5- once in a while or a little worried and concerned 6- hardly any of the time or hardly worried and concerned 7- none of the time or not worried and concerned

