6.9.5 Expected duration of each subject's participation

Subjects will be followed-up for 3 days since the initiation of the Petit Drill® syrup intervention.

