The patient's follow-up will last as long as he/she receives Petit Drill but will not exceed 3 days and 3 nights. Indeed, to stay close to real-word condition of use of Petit Drill, the treatment duration is recommended as per IFU but not imposed in the present clinical investigation. However, the parent must specify reason for stopping the treatment in the App.

During the follow-up, the patient's parent will have to complete the daily questionnaire and record Petit Drill intake in the App. Parents will be asked to inform the investigator of any adverse event as soon as possible.

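### The protocol does not settle whether follow-up ends when the syrup is stopped or runs a full 3 days, so third-night cough scores and solicited adverse events after an early stop may never be collected

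*Protocol*

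**What the plan says.** **Primary outcome.** Protocol 6.3.1 takes the final PCQ as follows: "Final value will rate the night following 3 day-treatment or the night following the day of stopping the treatment". It is collected the next morning, and the synopsis repeats the rule.

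**Early stopping is allowed.** Section 6.10: "the treatment duration is recommended as per IFU but not imposed in the present clinical investigation". The adherence row of Table 3 asks for the reason for an early stop and offers cough improvement, cough worsening or other.

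**Follow-up tied to use.** Section 6.10 and the synopsis: "follow-up will last as long as he/she receives Petit Drill but will not exceed 3 days and 3 nights".

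**Follow-up not tied to use.**
- 6.9.5: "Subjects will be followed-up for 3 days since the initiation of the Petit Drill".
- 6.1, on what parents record: "Any AEs that may occur during the 3-day/3-night follow-up period".
- The adverse event row of Table 3, section 8.1.2 (app entries) and section 14.3 (adverse events and device deficiencies) each give a 3-day period without a condition.
- Table 4 asks for each event's outcome when the 3-day follow-up ends.

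**Worded by treatment, so not decisive.** Table 3 times the last PCQ, VAS and PAC-QoL as "first thing in the morning after 3 rd night of treatment", and 14.1 speaks of the days of using the product. SO4 in 6.3.2 gives the PAC-QoL an early-stop alternative, "or on the next morning of the last day of treatment", which the Table 3 PAC-QoL row (D4 only) lacks.

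**The concern.** A parent may stop because the child is better or because the child is worse. The stop then fixes which night counts as final. Comparing the end-of-use rate with the rate on a common night would show how much the timing of stops shaped the result, but that needs a third-night PCQ from children who stopped early.

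Under 6.10 the app would not ask for it. Under 6.9.5 and the passages that agree with it, it would. The daily adverse event question is in the same position: under 6.10 a child who stops after one day has a shorter solicited window than one treated for three, and follow-up has ended before the date to which Table 4 refers.

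An analysis plan can define estimands and handle missing values, but it cannot recover entries that were never requested. So the collection rule has to be settled in the protocol.

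**Working it through.** **1. The plan's own precision.** With 95% confidence, p = 50% and half-width 7% (7.4), n = 1.96² × 0.25 / 0.07² = 196. With 20% dropout, 196 / 0.80 = 245. Both figures reproduce, and neither is affected by this point.

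**2. What 6.10 would leave.** The share s of children stopping early is not in the protocol, so these values are assumptions. Third-night values left = 196 × (1 − s); half-width = 1.96 × √(0.25 / n left).

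| s | values left | half-width (points) |
|---|---|---|
| 5% | 186 | 7.2 |
| 10% | 176 | 7.4 |
| 20% | 157 | 7.8 |
| 30% | 137 | 8.4 |

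For safety, with one prompt per day over 3 days, the share of child-days not solicited is s × (days lost) / 3. At s = 20% this is 20% × 2/3 = 13.3% if all stop after day 1, and 20% × 1/3 = 6.7% if all stop after day 2.

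**3. Which night is rated.** Suppose a parent sees the score for night 1 and stops on the D2 morning.
- If the day of stopping means the last dosing day (D1), the rated night is night 1, the same night that prompted the stop.
- If it means the calendar day of the decision (D2), the rated night is night 2, which comes after the prompt.

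On the D3 morning the two readings give night 2 and night 3.

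**4. Shift of the end-of-use rate from a fixed third-night (D4) rate.** This is a simulation on assumed inputs, because the protocol gives neither a stopping rate nor PCQ variability. Five items scored 0–5 with mean 2.5; SDs 0.8 between children, 0.6 between nights, 0.7 item noise; children kept if IC5 is met at baseline. Improved means a drop of at least 3, which is also the responder definition; non-improved means a score at or above baseline. Eligible families stop with chance q on each of the D2 and D3 mornings. The cough either does not change (D4 rate 42.9%) or falls by 0.3 per item per night (D4 rate 79.6%).

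Last-dosing-day reading, shift in points:

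| Who stops | trend | q = 5% | 10% | 25% | 50% |
|---|---|---|---|---|---|
| improved only | none | +1.8 | +3.4 | +8.4 | +15.8 |
| non-improved only | none | −1.0 | −2.0 | −5.0 | −9.4 |
| both equally | none | +0.7 | +1.4 | +3.3 | +5.9 |
| improved only | falling | +0.8 | +1.6 | +3.7 | +7.1 |
| non-improved only | falling | −1.4 | −2.7 | −6.6 | −12.6 |
| both equally | falling | −0.5 | −1.1 | −2.7 | −5.4 |

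With no trend and only improved children stopping, q = 10% means 8% of children stop. All of them count as responders, and the +3.4 shift implies that about 3.4 / 8 = 43% of them would not be responders on night 3.

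Calendar-day reading: with no trend the shift is within 0.1 points at every q. With a falling trend it is −0.2 to −0.4 at q = 5%, −0.9 to −2.1 at 25% and about −2 to −4 at 50%.

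Over 24 parameter settings, the last-dosing-day reading gives −1.6 to +1.8 points at q = 5% and −3.0 to +3.6 at 10%. If improved and non-improved children stop with equal chance, the shift stays within 0.8 and 1.6 points respectively.

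**The case against.** The strongest reply is that a coherent end-of-use reading exists. Only 6.10 and the synopsis address how stopping affects follow-up, and they set a ceiling. Section 6.9.5 is headed as an expected duration and could be nominal. The Table 3 schedule is labelled as suggested and runs by nights of treatment, 14.1 is tied to use, and SO7 counts relevant events during treatment. This stands for 14.1 and for the PCQ, VAS and PAC-QoL rows. It does not stand for 6.9.5, which counts from initiation, or for Table 4, which presupposes a 3-day end date. No passage says which rule governs.

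A reader might infer more than the text supports:
- That early stoppers have no primary value. They do: the PCQ for "the night following the day of stopping the treatment".
- That an end-of-use endpoint is an error. A descriptive study of real use, with no hypothesis (5.2) and no pass/fail rule (7.5), may choose it. No listed outcome asks for a D4 responder rate regardless of use, so that rate is an added sensitivity figure.
- That only spontaneous safety reports remain after a stop. Table 3 also schedules the question at investigation end, and 6.10 asks parents to report any event promptly.
- That stops go unrecorded. Table 3 captures the reason.
- That the result is distorted by 7 points or more. That needs frequent, mainly one-directional stopping and the last-dosing-day reading. IC6 selects families able to give the doses on all 3 days, and nothing in the protocol supports the high values of q.

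**Conclusion.** The contradiction over the follow-up window is real and worth an amendment. It leaves open whether third-night PCQ values and solicited adverse event answers exist for children who stop early. If they do not, nothing shows how far outcome-related stopping shaped the primary rate, and children do not share one solicited safety window.

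Size and direction are unknown. The nearest figure in the protocol, compliance of 83–95% with this product in the earlier European study (3.3.3), is not an early-stopping rate. On the assumed inputs, low stopping rates shift the end-of-use rate by up to a few points if the rated night follows the last dosing day, and by much less if it follows the day of the decision. The result therefore depends heavily on a definition that 6.3.1 does not give. These shifts compare two different quantities; they do not measure error in the declared one. No decision rule turns on the point: what is affected is how the responder rate can be read and whether adverse event windows are equal.

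**What to change.** - **Collection.** Reconcile 6.10 and the synopsis with 6.1, 6.9.5, Tables 3 and 4, 8.1.2, 14.1 and 14.3. State that the PCQ, the VAS and the daily adverse event and device deficiency question continue through the D4 morning for every enrolled child whose consent stands, whether or not the syrup was stopped. Align the PAC-QoL row of Table 3 with SO4.
- **Definition.** State in 6.3.1 and the synopsis which night the day of stopping refers to. SO4's wording need not be adopted, since the last-dosing-day reading is the more outcome-dependent of the two.
- **Reporting.** Keep the end-of-use responder rate as primary. Report the D4 responder rate beside it as a sensitivity analysis, and tabulate early stops by day and reason.

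The cost is amendment wording and at most two more mornings of app entries for early stoppers. Some of them will not answer, and their D4 values will include nights without the syrup, which is why the D4 rate should not replace the primary. How families use or stop the product is unchanged.
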